3.7.3.1.2. Sensitivity Analysis on the Rate and Number of EEDS

Annualized EEDS rate will be analyzed by a negative binomial regression model. The logarithmic transformation of the time from the first dose of the double-blind study drug to the last EEDS assessment visit will be included in the model as the “offset” parameter. The model will adjust the baseline PANSS total score and drinking status. If the data are underdispersed, or if the negative binomial regression model does not converge, a Poisson regression model will be used instead of the negative binomial regression model. Dispersion will be evaluated from the

Pearson Chi-Square statistic. If the ratio of the Pearson Chi-Square statistic to the degrees of freedom is ≤ 1 which indicates no overdispersion, then a Poisson regression model will be used.

The descriptive statistics for the annualized rate of EEDS for each treatment group will be calculated as the total number of EEDS experienced in the group divided by the total number of subject-years on study. The descriptive statistics for the annualized rate of EEDS rate for an individual subject will be calculated as the number of EEDS for that subject divided by the number of subject-years and presented by the treatment group.

3.7.3.1.3. Additional Analysis on the Rate and Number of EEDS

Since the EEDS consists of a series of individual criteria, number and percent of subjects who met each individual criterion will be provided. The treatment groups will be compared by the logistic regression model adjusting for the baseline PANSS total score and drinking status.

In addition, the duration of IAC confirmed hospitalizations related to the underlying disease will be summarized by treatment group.

3.7.3.2. Proportion of Subjects with at least 1 Level Decrease in World Health Organization (WHO) Drinking Risk Level from Baseline to Week 24 of Double-blind Treatment (Study Week 27)

The alcohol consumption per day at each visit will be calculated based on the number of drinks per day as follows.

$$\text{Alcohol consumption per day} = \frac{\text{total number of drinks} \times 14 \text{ gram}}{\text{total number of days}}$$

The risk of the alcohol consumption will be categorized based on the alcohol consumption per day using the criteria in Table 1. Proportion of subjects with at least 1 level decrease in World Health Organization (WHO) drinking risk level³ from baseline to week 24 of double-blind treatment (study week 27) will be compared between two treatment groups using the logistic regression model based on LOCF (last observation carried forward) imputation for the missing data, that is, the last observed non-missing post-baseline value will be carried forward for the missing post baseline assessments. The model will include the treatment group as factor and adjust for the baseline PANSS total score and drinking status.

Table 1: Criteria for risk of alcohol consumption on a single drinking day

Risk Category	Males	Females
Abstinence	0 g	0 g
Low Risk	1 to 40 g	1 to 20 g
Medium Risk	41 to 60 g	21 to 40 g
High Risk	61 to 100 g	41 to 60 g
Very High Risk	≥ 101 g	≥ 61 g

3.7.4. Other Efficacy Endpoints

Other efficacy endpoints for the double-blind treatment period are:

- The proportion of subjects with psychosocial events indicative of exacerbation of symptoms during the double-blind treatment period
- The rate and number of psychosocial events indicative of exacerbation of symptoms during the double-blind treatment period
- Change from baseline in PANSS total Score, Positive Score, Negative Score, and General Psychopathology Score during the double-blind treatment period
- Change from baseline in Clinical Global Impression–Severity (CGI-S) score during the double-blind treatment period
- Clinical Global Impression–Improvement (CGI-I) score during the double-blind treatment period
- Complete response profile of drinking during the double-blind treatment period
- Change from baseline in visual analogue score (VAS) for perception of desire for alcohol during the double-blind treatment period

3.7.4.1. Proportion of Subjects with Psychosocial Events Indicative of Exacerbation of Symptoms during the Double-blind Treatment period

The proportion of subjects with psychosocial events indicative of exacerbation of symptoms (defined in [study protocol section 11.2¹](#)) will be analyzed similarly as the primary analysis of the primary efficacy endpoint ([Section 3.7.2.1](#)). The incidence rate will be estimated by Kaplan-Meier estimate. The treatment comparison will be performed using the log-rank test and hazard ratio will be estimated by the Cox proportional hazards model.

3.7.4.2. Rate and Number of Psychosocial Events Indicative of Exacerbation of Symptoms during the Double-blind Treatment Period

The annualized rate and number of psychosocial events indicative of exacerbation of symptoms will be analyzed in the same way as the rate and number of EEDS ([Section 3.7.3.1](#)).

3.7.4.3. Change from Baseline in PANSS Total Score, Positive Score, Negative Score, and General Psychopathology Score during the Double-blind Treatment Period

Change from baseline of double-blind period in PANSS total score and subscale scores will be analyzed using ANCOVA (analysis of covariance) model with treatment group as factor and corresponding baseline value as the covariates for the ITT population. The ANCOVA model will be based on the LOCF imputation.

In addition, PANSS total score will be summarized by visit for the open-label olanzapine population. Plot of mean PANSS total score over time from the open-label periods (as overall) and through the double-blind period (by treatment group) will be provided for the open-label olanzapine population.

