During the double-blind treatment period, subjects will complete an outpatient visit every 2 weeks. As indicated in the schedule of assessments (see [Table 1](#), [Table 2](#), and [Table 3](#)), at some of these visits, subjects will complete a number of clinical assessments, receive a 15-minute counseling intervention (see [Section 8.3.26](#)), and will receive a 2-week study drug supply (including extra medication in case the subject does not return to the study site on the scheduled day; see [Section 10](#)). Other visits will be only drug dispensing visits during which subjects will only receive a 2-week study drug supply. No clinical assessments will be completed at drug dispensing visits.

Subjects randomized to double-blind treatment will be followed for a minimum of 9 months and a maximum of 15 months. After the end of the double-blind treatment period, subjects will complete a 3-week safety follow-up period. The study will be stopped when the last subject randomized is scheduled to complete Visit 26. When the last subject is randomized, all subjects currently participating in the study will be informed of the target completion date of the study period. After the last double-blind treatment period visit, subjects will proceed to the safety follow-up period.

The duration of the double-blind period will be between 9 and 15 months, depending on when the study is stopped. The target completion date will be based on the number of subjects randomized with enrollment ending when approximately 270 subjects have been randomized. After the last subject is randomized, the end date of the study will be set to occur approximately 9 months later and subjects will be informed of the target completion date. Final

samidorphan/placebo dosing for these subjects will take place the night before their final visit of the double-blind treatment period. A subject who is prematurely discontinued from the study will proceed as described in [Section 7.4](#).

After a subject completes an ET Visit and/or the safety-follow-up period, follow-up clinical care may be provided for up to 3 months if the PI determines that it is medically indicated. This care may include payments for medication and up to 3 clinic (outpatient) visits.

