14.3.2. Other Efficacy Endpoints

Other efficacy endpoints will include (but are not limited to) the following:

- The rate and number of EEDS
- The proportion of subjects with psychosocial events indicative of exacerbation of symptoms during the double-blind treatment period
- The rate and number of psychosocial events indicative of exacerbation of symptoms during the double-blind treatment period
- Change from baseline in PANSS total and sub-scale score during the double-blind treatment period
- Change from baseline in CGI-S score during the double-blind treatment period
- CGI-I score during the double-blind treatment period
- Complete response profile of drinking during the double-blind treatment period
- Change from baseline in VAS score for perception of desire for alcohol during the double-blind treatment period

The statistical methods include, but are not limited to, the following: Negative binomial regression will be used to compare treatment difference in the number and rate of EEDS and the number and rate of psychosocial events indicative of exacerbation symptoms during the double-blind treatment period. Logistic regression will be used to compare treatment difference in the proportion of subjects with psychosocial events during the double-blind treatment period. An ANCOVA model with LOCF (last observation carried forward) approach will be used to compare treatment difference in change from baseline during the double-blind treatment period in PANSS total and sub-scale score, CGI-S and VAS score for perception of desire for alcohol. Wilcoxon rank sum test will be used to compare treatment difference in CGI-I score. Drinking profile will be analyzed by an Anderson-Gill model.

Additional efficacy endpoints and analysis methods may be defined in the Statistical Analysis Plan.

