3.7.4.4. Change from Baseline in CGI-S Score during the Double-blind Treatment Period

The analysis of change from baseline in CGI-S score during the double-blind treatment period will be ANCOVA and LOCF method for the ITT population, similar to [Section 3.7.4.3](#).

3.7.4.5. Clinical Global Impression–Improvement (CGI-I) Score during the double-blind Treatment Period

CGI-I scores will be analyzed based on the subject's by-visit responder status (≤ 2 versus > 2) using the logistic regression model based on LOCF imputation for missing data. The model will include the treatment group as factor and the baseline PANSS as the covariate.

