3.7.4.7. Change from Baseline in Visual Analogue Score (VAS) for Perception of Desire for Alcohol during the Double-blind Treatment Period

The analysis of change from baseline in VAS score for perception of desire for alcohol during the double-blind treatment period will be ANCOVA and LOCF method, similar to [Section 3.7.4.3](#).

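### Change in PANSS, CGI-S and VAS is analysed only by ANCOVA on LOCF values, with no analysis visit named and no missing-data sensitivity analysis

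*SAP*

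**What the plan says.** SAP 3.7.4.3 fits an ANCOVA to change in PANSS total and subscale scores in the ITT population, with treatment as factor and the baseline value as covariate: "The ANCOVA model will be based on the LOCF imputation". For CGI-S (SAP 3.7.4.4) the method "will be ANCOVA and LOCF method for the ITT population, similar to" the PANSS section. For the VAS (SAP 3.7.4.7) the analysis of change over the "double-blind treatment period will be ANCOVA and LOCF method, similar to" the same section. Protocol 14.3.2 agrees: "An ANCOVA model with LOCF (last observation carried forward) approach will be used to compare treatment difference" on all three measures.

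The one definition of LOCF is in SAP 3.7.3.2, for a drinking endpoint: "the last observed non-missing post-baseline value will be carried forward for the missing post baseline assessments". It sets no limit to visits that a subject was due to attend. LOCF is applied visit by visit for CGI-I (3.7.4.5) and for the categorical drinking endpoints (3.7.4.6.1). For PANSS, CGI-S and VAS no visit is named. SAP 6.1 also defines a last post-baseline value, one per subject.

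Under Protocol 8, subjects are "followed for a minimum of 9 months and a maximum of 15 months", with a common stop when the last subject randomized is due at Visit 26. Subjects due only nine months of treatment go from Visit 26 directly to Visits 39 and 40 (Protocol Table 2, footnote 1).

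The sensitivity analyses for dropout in SAP 3.7.2.2 concern the primary endpoint only.

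**The concern.** LOCF treats the last score before dropout as the score at a later time. If one arm loses subjects earlier, its scores are frozen earlier. If scores are also moving over time, the earlier freeze appears as a difference in mean change, even when both arms follow the same trajectory.

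Both conditions are plausible here, though neither is established.

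- **Unequal dropout.** Discontinuation for lack of efficacy, loss to follow-up and subject withdrawal together form EEDS criterion 7 (SAP 3.7.2). The plan assumes that 15% vs 30% of subjects will have an EEDS by 9 months.
- **A time trend.** Subjects enter within 6 months of an exacerbation, and some start olanzapine only at Visit 2, six weeks before randomization.

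These are the trial's only tested comparisons of continuous symptom and craving scores: CGI-I is dichotomised and PSP is descriptive. The SAP probes informative censoring for the primary endpoint and has no counterpart here.

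**Working it through.** **The plan's own figure.** The only sample-size figure concerns the primary endpoint. HR = ln(0.85)/ln(0.70) = 0.4556. Schoenfeld events = 4(1.960 + 1.282)²/(ln 0.4556)² = 68.03, rounded up to 69, against the stated 70. Power with 70 events is 90.8% at HR 0.4556 and 91.6% at HR 0.45. The figure reproduces. There is no such calculation for PANSS, CGI-S or VAS.

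**Inputs from the documents.** 135 per arm; two-sided 5% level; Visit 8 at study week 3 and Visit 26 at study week 39, so Visit 26 is double-blind week 36.

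**Assumptions, not in the documents.** SD of change 10; within-subject correlation 0.6; the same linear trend in both arms; exponential dropout unrelated to outcome, stated as cumulative percent by week 36.

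**Step 1, hand check of the bias.** With cumulative dropout d by week 36, mean time observed is 36·d/(-ln(1-d)) weeks:

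- 20%: 32.27 weeks
- 30%: 30.28 weeks
- 40%: 28.19 weeks

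The false difference is about (trend/36) × (difference in mean time).

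- 20% vs 30%: 1.99 weeks, giving -0.33 (trend -6) or -0.55 (trend -10).
- 20% vs 40%: 4.08 weeks, giving -0.68 or -1.13.

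**Step 2, simulation with no true effect (2,000 replicates), LOCF ANCOVA at week 36.**

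| Trend by week 36 | Dropout 20/30% | Dropout 20/40% | Dropout 30/30% |
|---|---|---|---|
| -6 | -0.31, 5.9% | -0.67, 8.4% | -0.04, 5.2% |
| -10 | -0.54, 8.2% | -1.04, 12.4% | 0.03, 5.0% |
| 0 | 0.00, 5.0% | 0.01, 4.9% | 0.02, 4.8% |
| +6 | 0.31, 5.0% | 0.68, 8.7% | 0.03, 5.3% |

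Each cell gives the mean difference in points and the rejection rate. The rates are of the expected size: SE = 10·√(2/135) = 1.217, so a shift of 0.67 gives Φ(-1.96 + 0.55) + Φ(-1.96 - 0.55) = 8.5%. The sign follows the trend.

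**Step 3, the alternative.** A repeated-measures likelihood model on observed values only (known compound-symmetry covariance, 400 replicates) was run for trends -6 and -10 with 20/30% and 20/40% dropout. It gave differences between -0.09 and 0.10 point and rejection of 4.5-6.0%, with Monte Carlo error of about 1 point on the rates.

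**Step 4, staggered follow-up.** At week 56, with equal 30% dropout, 24-month accrual and trend -6, LOCF gave 0.04 point and 6.2% rejection (400 replicates). The administrative end of follow-up alone creates no difference.

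**Step 5, visits never due.** First consent is May 2014 and last completion falls in 2017 (Protocol synopsis). Allow for screening and six weeks of open-label treatment at the start, and for nine months plus three weeks at the end. Randomization then runs for roughly 20 to 33 months, or 87 to 143 weeks. With uniform accrual, the share not due at double-blind week 48 (Visit 32) is (48 - 36)/accrual weeks: 12/87 = 14% down to 12/143 = 8%.

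**The case against.** The best reply has four parts.

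**The bias is conditional.** A reader might infer that unequal dropout alone makes LOCF produce a difference. It does not: in the zero-trend rows there is no bias and rejection stays at about 5%. Subjects are randomized after six weeks of open-label treatment, the olanzapine dose is normally fixed after Visit 5, and PANSS must be 50 to 80 at Visits 6 and 8. Any later trend may be small. This stands.

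**The dropout gap is assumed.** A 20-point gap exceeds the whole planned EEDS difference of 15 points. Discontinuation is one of eight criteria, and subjects with other events may continue. The 8-12% rejection range is therefore not a central estimate; with a 10-point gap it is 6-8%. This stands.

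**Filling of visits never scheduled is not stated.** A reader might infer that LOCF will impute Visits 28 to 38 for subjects who finished on time. The LOCF definition speaks of missing assessments, and one never due is arguably not missing. The SAP 6.1 definition permits one last value per subject, which fills nothing. Nor does staggered follow-up bias the comparison, because randomization balances it. A large never-due share, such as 12/26 = 46% at week 48, would require six-month accrual, which the protocol dates do not fit. What remains is that either reading leaves the time point undefined.

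**Tier and other displays.** These are classed as other efficacy endpoints, LOCF was prespecified in the protocol, and mean PANSS by arm over time will be plotted. That lowers the priority, but a plot is not a sensitivity analysis. A claim that standard errors are distorted is not supported either: equal-dropout runs reject at about 5%.

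**Conclusion.** The point holds in a limited form. The only planned tests of change in PANSS, CGI-S and VAS rest on LOCF, with no named visit and no check on missing data. LOCF misleads here if dropout is unequal and scores trend, or if dropout depends on outcome; the second route was not simulated.

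Under the stated assumptions, PANSS shifts by about 0.3 to 0.5 point for a 10-point dropout gap and 0.7 to 1.0 point for a 20-point gap. Rejection is 6-8% and 8-12% respectively. With equal dropout or no trend the shift is zero. The sizes rest wholly on assumed SD, trend and dropout.

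Separately, the time point is undefined. By-visit LOCF after Visit 26 could fill visits never due (about 8-14% of subjects at double-blind week 48), while one last value per subject would pool different durations.

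A reader might infer that the trial's main conclusion is at risk. It is not: the log-rank test and the 70-event calculation do not use these values. The change is worth making because it is cheap.

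**What to change.** In SAP 3.7.4.3, 3.7.4.4 and 3.7.4.7:

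- Make the main analysis an MMRM on observed scheduled double-blind visits through Visit 26, with treatment, visit, treatment-by-visit, baseline and baseline-by-visit. Every subject is due to reach Visit 26, and all three measures are scheduled there.
- Use an unstructured covariance and prespecify a fallback. PANSS has 10 post-randomization visits through Visit 26, hence 10 × 11/2 = 55 covariance parameters, and the fit may not converge.
- Name the treatment contrast at Visit 26 as the reported estimate.
- Keep LOCF ANCOVA at Visit 26 as a sensitivity analysis, which preserves the protocol's method.
- Add one missing-not-at-random sensitivity analysis, since the MMRM assumes missing at random and lack-of-efficacy dropout may violate that.
- Record the change from Protocol 14.3.2 in SAP section 5.

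The cost is SAP wording and some programming, with no new data. The downsides are the missing-at-random assumption and that visits after Visit 26 become descriptive.

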3.7.4.4. Change from Baseline in CGI-S Score during the Double-blind Treatment Period

The analysis of change from baseline in CGI-S score during the double-blind treatment period will be ANCOVA and LOCF method for the ITT population, similar to [Section 3.7.4.3](#).

3.7.4.5. Clinical Global Impression–Improvement (CGI-I) Score during the double-blind Treatment Period

CGI-I scores will be analyzed based on the subject's by-visit responder status (≤ 2 versus > 2) using the logistic regression model based on LOCF imputation for missing data. The model will include the treatment group as factor and the baseline PANSS as the covariate.

3.7.4.6. Complete Response Profile of Drinking during the Double-blind Treatment Period

Complete response profile of drinking during the double-blind treatment period will be analyzed by the following endpoints:

- Proportion of subjects with at least 1 level decrease in World Health Organization (WHO) drinking risk level from baseline by visit
- Proportion of subjects with at least 2 levels decrease in World Health Organization (WHO) drinking risk level from baseline by visit
- Proportion of subjects abstinent from heavy drinking days from randomization through week 24 of the double-blind treatment period (study week 27)
- Proportion of subjects abstinent from heavy drinking days by visit
- Proportion of subjects abstinent from drinking days by visit
- Number and rate of heavy drinking days
- Number and rate of drinking days
- Percent of heavy drinking days cumulatively from baseline through weeks 12, 24, 36, 48 and 60 of the double-blind treatment period
- Percent of drinking days cumulatively from baseline through weeks 12, 24, 36, 48 and 60 of the double-blind treatment period
- Percent of heavy drinking days by visit during the double-blind treatment period
- Percent of drinking days by visit during the double-blind treatment period
- Number of drinks per day by visit during the double-blind treatment period
- Number of drinks per drinking day by visit during the double-blind treatment period

In general for the TLFB assessment, by-visit result is defined as the drinking assessments between previous and current visits. It will be 2 weeks of drinking assessments for Visit 9 Week 5 and Visit 10 Week 7, and monthly thereafter.

3.7.4.6.1. Categorical endpoints for the Complete Response Profile of Drinking

The following categorical endpoints for the complete response profile of drinking during the double-blind treatment period will be analyzed using a logistic regression model.

- Proportion of subjects with at least 1 level decrease in World Health Organization (WHO) drinking risk level from baseline by visit
- Proportion of subjects with at least 2 levels decrease in World Health Organization (WHO) drinking risk level from baseline by visit
- Proportion of subjects abstinent from heavy drinking days from randomization through week 24 of the double-blind treatment period (study week 27)
- Proportion of subjects abstinent from heavy drinking days by visit
- Proportion of subjects abstinent from drinking days by visit

The model will include treatment as factor and adjust for baseline PANSS and drinking status. LOCF imputation will be used for the by-visit summary.

3.7.4.6.2. Number and Rate of Heavy Drinking Days or Drinking Days

Considering heavy alcohol drinking days or drinking days as recurrent events, an Anderson-Gill model will be used to analyze the time-to-recurrent events, similar to [Section 3.7.3.1.1](#).

Weekly alcohol drinking and heavy drinking rate will be summarized by treatment groups and compared by the negative binomial model, similar to [Section 3.7.3.1.2](#).

3.7.4.6.3. Percent of Heavy Drinking Days or Drinking Days Cumulatively through Weeks 12, 24, 36, 48 and 60 of the Double-blind Treatment Period

Percent of heavy drinking days or drinking days cumulatively through weeks 12, 24, 36, 48 and 60 of the double-blind treatment period (corresponding to study weeks 15, 27, 39, 51 and 63) will be compared between two treatment groups using the Wilcoxon rank sum test.

Cumulative frequency distributions of percent of heavy drinking days or drinking days through week 60 of the double-blind treatment period will be presented by treatment group with horizontal axis as percent of heavy drinking days and vertical axis as corresponding proportion of subjects in each treatment group.

Two sensitivity analyses will be conducted. First analysis will exclude any drinking records after the discontinuation of the double-blind study drug or after any forced abstinence to control for carryover effects. Forced abstinence is defined as greater than 4 days of hospitalization or any incarceration. Additional sensitivity analysis will exclude any drinking records after discontinuation of the double-blind study drug or incarceration or 1 week of drinking records after greater than 4 days of hospitalization.

3.7.4.6.4. Percent of Heavy Drinking Days or Drinking Days by Visit during the Double-blind Treatment Period

Percent of alcohol heavy drinking days or drinking days will be presented by visit and by treatment groups. In addition, plot of mean percent of heavy drinking days or drinking days by

visit from the open-label periods (as overall) and through the double-blind period (by treatment group) will be provided for the open-label olanzapine population.

3.7.4.6.5. Number of Drinks Per Day and Per Drinking Day by Visit during the Double-blind Treatment Period

Number of drinks per day and per drinking day during the double-blind treatment period will be summarized by the treatment group and by visit.

3.7.4.7. Change from Baseline in Visual Analogue Score (VAS) for Perception of Desire for Alcohol during the Double-blind Treatment Period

The analysis of change from baseline in VAS score for perception of desire for alcohol during the double-blind treatment period will be ANCOVA and LOCF method, similar to [Section 3.7.4.3](#).

